13.5.5 Definition of End of Study

The end of this study is defined as 30 days after the date when the last recruited participant has been discharged from the Emergency Department i.e. the last data point has been collected for the last study participant.

14.0 STATISTICAL ANALYSIS PLAN

14.1 Rationale

According to the Office of National Statistics report on the results of the 2021 Census⁷, the population of Cambridge is approximately 146,000 people. Of this population, around 75% classed their ethnicity as White (comprising the following categories: British, Irish, Roma, Gypsy or Irish Traveller, or Other) and around 15% are children aged 15 years or less. For this clinical study, it is expected approximately 20% of participants will be less than 16 years of age, and the majority of participants will be white Caucasian, providing a casemix with external validity in line with the demographics of the catchment area.

This prospective paired diagnostic accuracy and economic evaluation study is designed to assess the clinical performance and potential health system impact of a new molecular Point Of Care Test for respiratory infections in the Emergency Department (ED) setting. The new Logicore System testing device detects six key respiratory pathogens including four infections currently targeted by the current gold standard test (Cepheid); Influenza A (Flu A), Influenza B (Flu B), Respiratory Syncytial Virus (RSV) and SARS-CoV-2. The Logicore System device detects two additional pathogens not included in the established POCT; *Mycoplasma pneumoniae* (MP) and human adenovirus (HAdV).

During the winter season planned for this study, the overall positivity of the current POCT for respiratory disease is estimated at 30-50% of those selected by the respiratory criteria for the standard test (CUH personal communication). However, it is recognised that infections do not distribute evenly by age, or season, or time of the season. For example, RSV is more common in the very young or elderly and has peaks later in the winter months. Thus, the statistical approach to assessment requires us to estimate how many true positives per infection type* might be expected to achieve a sensitivity of 95% with a 10% margin of error, not just overall.

Also, during the winter season, disease type incidence will occur in runs and hence it is possible to inadvertently populate the whole study with one type of infection.

Logically our total sample size will need to be calculated on the lowest prevalence infection. As this is planned as an Intention To Treat study (ITT), i.e. including clinical benefits, then 10-15% extra samples would provide a reasonable margin of samples to allow for withdrawals and invalid samples.

*Table showing impact of variable distribution of infection type on defining sample numbers (after CUH data)

Infection	Estimated Prevalence in	Number Needed for 19
	Winter Population	Positives
RSV	~15%	~127
Flu A	~10%	~190
Flu B	~5%	~380
SARS-CoV-2	~10%	~190

As the basis of this study is to determine sensitivity of the Logicore System testing device, rather than combined diagnostic performance across all four infections (rather than each one separately) then we need to apply this distribution imbalance to the way we calculate the minimum sample number to ensure at least achieving our sensitivity goal for each pathogen.

All eligible participants, i.e. those selected by the respiratory and inclusion criteria noted above with respiratory symptoms and a signed consent form, will be enrolled in the study. Using dual swabs, respiratory samples will be collected simultaneously for use in both new (Logicore System) and gold standard (Cepheid) tests to ensure comparability. This method will reduce the risk that differences in test outcomes are the result of inequitable sampling.

The aim also is to use the inclusion/exclusion criteria to recruit consecutive patients in the ED, suspected of the target condition to attempt to reduce spectrum bias. This real-world sample ensures external validity.

As this POCT occurs in a real time ITT setting, sample swabs will be handled consecutively within a few minutes to enter them into the POCT devices with no delay before and between test commencing. Both devices are expected to deliver a result with a similar elapsed time envelope. Hence commonly both tests will be running in parallel at any moment and model more closely the normal pathways of care in use.

This study is primarily aimed at validating the performance of a new POCT device (Logicore System) against an existing POCT device (Cepheid). This is the basis for this statistical plan rather than using a reference standard/composite diagnostic test e.g. PCR + Chest X-Ray.

Blinding the study will be difficult because of the situation of the study.

With regards to incorporation bias, the new test result will not influence the gold standard result.

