This study aims to recruit participants during the winter months, when the gold standard POCT device used at CUH is the Cepheid multiplex PCR assay (known as GeneXpert). This test can produce results in around 40 minutes to an hour. The advantage of utilising the Logicore System is that it can test for 2 additional pathogens in roughly the same amount of time as Cepheid (it takes 63 minutes to produce the results) but is expected to be more sensitive to the pathogens (for example, the minimum limit of detection is 131 copies/mL for SARS-CoV-2 using Cepheid³ but is expected to be only 100 copies/mL for the same pathogen using the Logicore System). This could alleviate the need for additional UK HSA laboratory testing if a patient was admitted following a negative Cepheid test but continued to exhibit respiratory symptoms, as it is more likely the pathogen would be identified in the initial Logicore System testing process. The CUH IPC Guideline instructs that patients with suspected respiratory infection should be isolated while further UK HSA lab PCR testing is performed. Therefore, the improved sensitivity in diagnostic capability could reduce the need for unnecessary isolation of patients as there would be reduced requirement for the secondary HSA testing. Conversely, the improved turnaround time would ensure rapid instigation of appropriate isolation procedures when a patient has positive initial results to reduce the spread of infection in the ED, in conjunction with quicker treatment of patients with targeted therapeutics medicinal products.

This study aims to produce evidence to support the Logicore System claims of increased sensitivity and specificity, whilst maintaining accuracy, and reduced turnaround times Version 1.0 dated 09/OCT/2025 CONFIDENTIAL Page 13 of 49

compared to current practice, and to provide the Trust with a Cost Benefit analysis from assessment with the Logicore System.

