11.0 STUDY DESIGN

This is a prospective, single-centre, diagnostic accuracy study, being conducted at Addenbrooke's Hospital in Cambridge. Participants can be any age but must exhibit acute respiratory symptoms on presentation at the Emergency Department and require standard of care diagnostic testing as per CUH Trust IPC policy.

The study will be performed in accordance with the Declaration of Helsinki⁵, principles of Good Clinical Practice⁶ and local and regulatory requirements.

The study is aiming to recruit 400 participants. There is no Investigational Medicinal Product involved and therefore no treatment arms and no randomisation. Swab samples taken from each participant will be tested by standard POCT (control data) and by Logicore System POCT device.

Members of the research ream will utilise Personal Protective Equipment (PPE) in line with the CUH Infection Prevention and Control Guideline.

There is only one visit required for each participant, during which the following data will be collected:

- Study identifying number
- Date of Visit and Study Assessments (presentation at ED)
- Sex
- Age in years
- Emergency Care Data Set (ECDS) presentation code
- Clinical signs and symptoms of respiratory tract infection
- Date of onset of clinical symptoms of respiratory tract infection
- Time nasopharyngeal swabs taken
- Time results available from Cepheid and Logicore System devices (to establish turnaround time in minutes)
- Hospital admission required? Y/N
- Intensive care admission required? Y/N
- NEWS-2 Score for participants 15 years of age and above
- PEWS (Paediatric Early Warning Score) for participants less than 15 years of age
- Arrival by ambulance? Y/N
- Respiratory rate (breaths per minute)
- Temperature (in °C)
- Heart rate (beats per minute)
- Blood pressure (systolic and diastolic)
- Oxygen saturation (%)
- Confirmation that Logicore System Instructions For Use (IFU) were followed to test the sample using the new device
- Participant and staff assessment of acceptability
- Adverse event details.

Following discharge from the ED (to home, nursing home or a hospital ward etc), the following additional information will be collected:

- 7, 14 and 30-day mortality
- Discharge diagnosis confirmation.

To assess the acceptability of the testing process, each participant will be asked the following question:

'How unpleasant was the swab'?

The participants must rate the swabbing process according to the following categories:

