13.5.3 Study Sample Collection and Testing Process

Study staff undertaking the sample collection will wear appropriate personal protective equipment (PPE) for the risk exposure at all times, in line with CUH local guidelines for Infection Prevention and Control. To eliminate potential differences in the samples being tested, two nasopharyngeal swabs will be collected simultaneously. One swab will be tested by the gold standard Cepheid multiplex POC test (i.e. standard of care diagnostic testing as required by CUH Trust IPC policy) and the other with the novel Logicore System multiplex POC device. The Logicore System swab will be tested using a specific Logicore System buffer which will be provided for use in a closed vial by the Sponsor. The testing of each specimen (Cepheid or Logicore) must begin within 20 minutes from the time of swab collection, according to the specimen processing guidelines. There is no need to store the swabs/buffer solutions on ice. These can remain at ambient temperature for storage.

The Cepheid POCT is done in the laboratories above the ED. The Logicore System (i.e. the Analytical Module into which the Respiratory Pathogen Panel cartridge is loaded for analysis and the portable Operation Module with display screen, into which the cartridge details and participant anonymised details are input) will be located in a secure clinical area within the ED, with controlled access.

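### Section 14.1 sets blinding aside with no reason or safeguard, although masked recording of the Logicore run is feasible and decisions on which runs count may be made with the Cepheid result known

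*Protocol*

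**What the plan says.** On blinding, Section 14.1 says only "Blinding the study will be difficult because of the situation of the study". The next sentence protects one direction: the new test is not to affect the gold standard result. The opposite direction, from a known Cepheid result to the Logicore record, is not mentioned.

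On the set-up, Section 13.5.3 states "The Cepheid POCT is done in the laboratories above the ED", whereas the Logicore equipment "will be located in a secure clinical area within the ED, with controlled access". Section 7.2 has the Logicore result appear on the screen of its own Operation Module.

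On which runs count:
- The per-participant data list in Section 11.0 includes "Confirmation that Logicore System Instructions For Use (IFU) were followed to test the sample using the new device". It gives no time for this entry and lists no counterpart for the Cepheid run.
- Rule A under Figure 1 (Section 11.0) counts a Cepheid-positive, Logicore-negative pair as a Logicore false negative.
- The estimand table (Section 14.6) names an invalid swab or test as an intercurrent event for the primary objective. It does not say who judges validity or what that person may have seen.
- Section 16.9.1 leaves it to the sponsor to decide whether data affected by an uncorrectable deviation stay in the analysis.
- Section 18.1 allows a week for eCRF entry.

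On timing, Section 7.1 says of Cepheid "This test can produce results in around 40 minutes to an hour" and of Logicore "it takes 63 minutes to produce the results". Under Section 13.5.3 each test "must begin within 20 minutes from the time of swab collection". Section 14.1 adds: "Both devices are expected to deliver a result with a similar elapsed time envelope".

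**The concern.** In a paired accuracy study, the person who settles whether an index-test run is usable should not know the comparator's answer. Here the protocol takes a position on blinding, gives no specific reason for it, and describes a layout that would make masked recording easy. It then leaves three decisions about the Logicore run open to someone who may know the Cepheid result: whether the instructions were followed, whether the run was valid, and whether deviating data are kept.

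The primary endpoint is at stake. If a Logicore miss is more likely to be examined, and then set aside, because it disagrees with Cepheid, sensitivity rises for reasons unrelated to the device. The instruction-compliance entry exists for Logicore only, so the scrutiny is uneven. The exclusion decision lies with the sponsor, which is the UK subsidiary of the manufacturer (Section 7.2), looks at data as they accrue (Section 16.8) and analyses them (Section 16.10). None of this implies intent; it is why a rule should be written down.

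**Working it through.** **1. Is masked recording feasible?** The two tests run in different places (Section 13.5.3), and the Logicore result comes up on its own screen (Section 7.2). Nothing described requires the Logicore operator to see the Cepheid result before recording. Rule C in Section 11.0 does need both results, to decide on second-line testing, so the care pathway cannot be blinded throughout. That comparison comes after the Logicore result exists, so recording first and comparing second is compatible with it.

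**2. How could a miss leave the analysis?** Not through classification, because Rule A makes it a false negative with no exception. Two routes remain: the run is treated as invalid (Section 14.6), or the data are excluded after a deviation (Section 16.9.1), for which the instruction-compliance entry could supply the grounds. On the first, Section 14.1 wants 10–15% extra samples to cover withdrawals and invalid samples, which suggests that invalid runs drop out. Neither route has to be decided without sight of the Cepheid result, and the one-week eCRF window means that both results would ordinarily be available by then.

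**3. Reproducing the plan's figures.** From Section 14.3.1, n = Z²P(1−P)/d² = 1.96² × 0.95 × 0.05 / 0.10² = 18.25, rounded up to 19. Then 19/0.05 = 380, and 380 + 20 = 400. These agree with the protocol and are not in dispute.

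**4. Size per removed miss.** Expected positives are 400 times the prevalence in the Section 14.1 table; expected detections are 95% of those. Removing one miss changes sensitivity from TP/n to TP/(n−1).

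| Pathogen | Positives | Sensitivity | One miss removed | Change (points) |
|---|---|---|---|---|
| Flu B | 400 × 0.05 = 20 | 19/20 = 95.0% | 19/19 = 100% | +5.0 |
| Flu A, SARS-CoV-2 (each) | 400 × 0.10 = 40 | 38/40 = 95.0% | 38/39 = 97.4% | +2.4 |
| RSV | 400 × 0.15 = 60 | 57/60 = 95.0% | 57/59 = 96.6% | +1.6 |

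For Flu B, one removal is half the planned 10-point precision and deletes the only expected miss.

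**5. Which result is known first?** With simultaneous starts, Cepheid finishes 63 − 60 = 3 to 63 − 40 = 23 minutes ahead. Assume independent start delays, uniform over 0–20 minutes, and a Cepheid run uniform over 40–60 minutes. Simulation then has Cepheid's machine result first in about 90% of pairs. That is machine finish, not knowledge in the ED. Adding an assumed reporting lag:

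| Lag (min) | Cepheid known first |
|---|---|
| 0 | 90% |
| 5 | 78% |
| 10 | 61% |
| 15 | 43% |
| 20 | 25% |

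The delay distributions and lags are assumptions; the protocol gives neither.

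**The case against.** The best defence is that the instrument produces the result, so the usual reason for blinding, subjective reading, is largely absent; that Rule A already fixes how a miss is scored; and that Cepheid is routine care whose result cannot be withheld from the ED. All three stand. They narrow the point to which runs count, and they explain why full blinding is hard. They do not explain why the Logicore record cannot be made first.

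Stronger readings are tempting, and the documents do not support them:

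- *Staff usually know the Cepheid answer when they complete the Logicore fields.* No section says who completes them, when, or when the Cepheid result reaches that person. Run times point that way, but a lag of about 15 minutes reverses the order, and Section 14.1 itself expects similar times. Separate floors make prior knowledge less likely, not more. The synopsis gives up to 90 minutes for current laboratory testing, but Section 8.2 attributes an hour and a half to the second-line test, so that figure does not settle the matter.
- *A miss can simply be relabelled as user error.* Rule A has no such exception, no section says that a negative compliance entry removes a result, and in Section 14.6 user error appears only under turnaround time.
- *Validity is a matter of staff opinion.* The protocol does not say whether invalid runs are flagged by the device or by staff.
- *Cepheid runs face no check.* The 20-minute start rule and the deviation review apply to both tests, and Section 14.6 lists an indeterminate gold standard. Only the instruction-compliance entry is confined to Logicore, and an extra check on a newly introduced device is ordinary practice.

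**Conclusion.** The point holds in a limited form. Section 14.1 sets blinding aside without a reason or safeguard where masked recording of the index test is feasible, and it guards only against influence from Logicore to Cepheid. The remaining bias route runs through instruction compliance, run validity and sponsor exclusions, each of which may be decided with the Cepheid result known. It does not depend on which machine finishes first, because Sections 16.9.1 and 18.1 allow these decisions and entries to be made later.

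The size is 1.6 to 5.0 percentage points of sensitivity per miss removed, assuming 400 participants, the protocol's prevalences and a true 95% sensitivity. This illustrates the effect of a removal and does not predict how often one will occur; the documents give no basis for a frequency. It does not invalidate the design, but a cheap safeguard would close an avoidable risk that tends to favour the new device on the primary endpoint.

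**What to change.** Replace the blinding sentence in Section 14.1 with a statement that the care pathway is not blinded but the index-test record is:

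- compliance with the Logicore instructions is recorded when the cartridge is loaded;
- Logicore validity and result are time-stamped, on the source document or by export from the Operation Module, before the person recording them views the Cepheid result.

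Add to Section 16.9.1 that decisions to exclude data from either test are made without sight of either test's result and under the same criteria for both. Reordering data entry alone would not be enough, because it would not stop a later exclusion made with both results in view.

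The cost is slightly more real-time recording discipline for up to 400 participants and one training point. No extra staff or procedures are needed. The one-week eCRF window can stay, since the time stamp may sit on the source record, and the Cepheid result still reaches the care team as usual.

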14.2 Study Endpoints

14.2.1 Specificity (or Sensitivity)

The Primary Endpoint is to demonstrate the sensitivity and diagnostic accuracy of the new Logicore System POCT device compared to the current gold standard (Cepheid) for the four overlapping infections. Based on an expected sensitivity of 95% and a 10% allowable margin, approximately 19 positive cases per infection are required to estimate sensitivity with a 95% confidence. Assuming a positivity rate of up to 50% based on the selection criteria, 400 patients will ensure sufficient numbers of true positive cases for each pathogen and enable accurate estimation of sensitivity, specificity and predictive values for both tests. The paired design allows for direct comparison of the new and established test results using McNemar's test and Cohen's Kappa.

As a secondary component we will evaluate turnaround time, patient and staff acceptability of the new test, and Cost-Benefits of the new test device.

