14.3.1 For Sensitivity (or Specificity)

$$n=(Z^2.P.(1-P))/d^2$$

n = number of diseased (or non-diseased) subjects required

Z = 1.96 for 95% confidence (the assumption is that this approach could apply to either sensitivity or specificity but here we expect sensitivity will require the higher resolution)

P = expected sensitivity (or specificity) (0.95) for two tailed test

d = desired precision (0.10)

Samples needed for positive cases (sensitivity):

n = 18.2 >>> 19 cases.

From our above table our minimum expected prevalence for any one type of disease is 5% and our maximum is 15% so we can easily estimate what sample total will most likely deliver 19 cases.

If prevalence is low:

N = n/prevalence = 19/.05 = 380 cases.

If the prevalence is uniformly high:

N = n/prevalence = 19/.15 = 127 cases.

This gives us a range of sample size which allows for this variable prevalence. If we assume the worst prevalence state, then 380 cases are required and a further 20 might provide additional safety to achieve a 19-event incidence for each type of infection.

Thus, the recommendation is for a trial recruiting **400** participants.

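### For Flu B, the infection the study is sized on, 400 participants neither assure 19 positives nor give a 10-point margin on sensitivity, and the plan's own 10-15% allowance is not in the total

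*Protocol*

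**What the plan says.** Section 14.1 bases the total on the least prevalent infection. Its table gives winter prevalences of about 15% for RSV, 10% for Flu A, 5% for Flu B and 10% for SARS-CoV-2, and says the sensitivity goal is to be met for each pathogen. It puts overall positivity at 30-50%. It also says that "10-15% extra samples would provide a reasonable margin of samples to allow for withdrawals and invalid samples".

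Section 14.2.1 states: "Based on an expected sensitivity of 95% and a 10% allowable margin, approximately 19 positive cases per infection are required". It then concludes that "400 patients will ensure sufficient numbers of true positive cases for each pathogen".

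Section 14.3.1 gives the calculation: a normal-approximation precision formula with "Z = 1.96 for 95% confidence", expected sensitivity 0.95 and precision 0.10, leading to "n = 18.2 >>> 19 cases". Dividing by the 5% prevalence gives 380. The section then adds that "a further 20 might provide additional safety to achieve a 19-event incidence for each type of infection", and recommends 400.

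Section 13.3 replaces participants who withdraw before sampling, or who withdraw afterwards and have the research sample destroyed. It does not mention replacing invalid tests. The estimand table in 14.6 lists invalid swabs or tests, and indeterminate gold-standard results, as intercurrent events.

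**The concern.** Three things are stated more strongly than the calculation allows. First, dividing 19 by the prevalence gives the number of participants at which 19 positives are expected. That is not a number at which 19 are assured, and 14.3.1 itself uses weaker language about the extra 20 than 14.2.1 uses about the total. Second, the formula is a normal approximation applied where only about one missed case is expected (19 × 0.05 = 0.95), which is where that approximation breaks down. Third, the 20 participants added are fewer than the 10-15% that 14.1 calls reasonable, and 14.3.1 assigns them to the event count, not to losses.

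Flu B sensitivity is one of four per-pathogen primary results. A reader of the protocol would expect it to be known to within 10 points and would not expect a shortfall in cases. Neither expectation is safe.

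**Working it through.** **Inputs.** Z = 1.96, P = 0.95, d = 0.10 (14.3.1). Prevalences 15%, 10%, 5%, 10% (14.1 table; they sum to 40%). Overall positivity 30-50% (14.1). Allowance 10-15% (14.1). N = 400.

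**1. The plan's figure.** n = Z²P(1−P)/d² = 1.96² × 0.95 × 0.05 / 0.01 = 18.25, rounded up to 19. Then 19/0.05 = 380, and 380 + 20 = 400. All reproduce.

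**2. Chance of reaching 19 Flu B positives.** With X ~ Binomial(N, p), the expected count at N = 400 and p = 0.05 is 20, and P(X ≥ 19) = 0.623. At N = 380 it is 0.533. For infections at 10% or 15%, it exceeds 0.999 at N = 400.

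To reflect 30-50% positivity, scale the table's mix, keeping proportions fixed (an assumption; the plan does not give the mix at other positivity levels):
- 30%: Flu B = 5% × 30/40 = 3.75%, P(X ≥ 19) = 0.18
- 40%: Flu B = 5%, P(X ≥ 19) = 0.62
- 50%: Flu B = 5% × 50/40 = 6.25%, P(X ≥ 19) = 0.91

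The binomial treats participants as independent. Section 14.1 says infections come in runs, which would make the count more variable.

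**3. Margin with 19 positives.** By the plan's formula the half-width at n = 19 is 1.96 × √(0.95 × 0.05/19) = 0.098. But at 18/19 the Wald interval runs to 104.8%. At 19/19, which has probability 0.95¹⁹ = 0.38, it has zero width. Its actual coverage at n = 19 and true sensitivity 0.95 is 62%, not 95%.

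Intervals with sounder coverage at 18/19 (94.7%):
- Clopper-Pearson: 74.0-99.9%, half-width 12.9 points, lower limit 20.8 points below the estimate
- Wilson: 75.4-99.1%, half-width 11.9 points, lower limit 19.4 points below

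Positives needed at 95% observed sensitivity: about 29 (exact) or 25 (Wilson) for a half-width of 10 points; about 52 (exact) or 49 (Wilson) for a lower limit no more than 10 points below the estimate.

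**4. Per pathogen at N = 400 and the tabulated prevalences, 95% observed.**

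| Infection | Expected positives | Exact 95% limits | Half-width (points) |
|---|---|---|---|
| RSV | 60 (57/60) | 86.1-99.0% | 6.4 |
| Flu A, SARS-CoV-2 | 40 each (38/40) | 83.1-99.4% | 8.2 |
| Flu B | 20 (19/20) | 75.1-99.9% | 12.4 |

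**5. Allowance.** 380 × 1.10 = 418 and 380 × 1.15 = 437. The plan adds 20/380 = 5.3%. If 10% or 15% of 400 were lost and not replaced, 360 or 340 would be evaluable. At 5% prevalence, expected Flu B positives would be 18 or 17, and P(X ≥ 19) would be 0.44 or 0.34.

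**The case against.** The strongest defence is that nothing has been miscalculated. The formula belongs to the diagnostic sample-size methods named in 14.3, and every figure follows from it. That stands: the fault is in what the figures are said to deliver. It is also true that with 19 positives and true sensitivity 95%, the observed proportion falls within 10 points of 95% with about 93% probability. That describes the scatter of the estimate. It does not make the 95% confidence interval ±10 points wide.

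A second defence is that 14.2.1 assumes positivity of up to 50%. If that level applied throughout with the same mix, the Flu B probability would be 91%, and 81% or 72% after 10% or 15% loss. This is a fair reason to show the range and not only its low end. It still falls short of an assurance.

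Third, section 13.3 replaces some withdrawals, so part of the 10-15% is already covered. The 44% and 34% figures hold only if the whole 10-15% were unreplaced losses, in practice mainly invalid tests. Section 14.4 offers to consider an early assessment if prevalences are far out, but commits to no extension.

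A reader might infer more than the documents support:
- That only RSV reaches the stated precision. In the plan's formula d is a half-width, and on that definition Flu A and SARS-CoV-2 also meet it. RSV stands alone only if the margin is redefined as the distance down to the lower limit.
- That 400 has no other basis. Section 14.3.4 also relies on about 400 patients for the cost-effectiveness analysis.

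**Conclusion.** The point holds for Flu B. At N = 400 the plan's own target of 19 Flu B positives is reached with probability 62% at exactly 5% prevalence, within a range of 18% to 91% over the stated positivity. At 19 or 20 positives the interval is wider than the stated margin: half-width 12.9 points exact or 11.9 Wilson at 18/19, and 12.4 exact at 19/20. The allowance contained in 400 is 5.3%, against the 10-15% the plan calls for.

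The other three infections are secure at the tabulated prevalences, both in case numbers and in half-width. The conclusion therefore does not extend to the study as a whole being too small. It rests on binomial counts with independent participants, on 95% observed sensitivity, and, for the 18-91% range, on a fixed mix of infections.

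**What to change.** Keep 400 and correct what is claimed for it.

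- In 14.2.1 and 14.3.1, replace the assurance with the probability of at least 19 Flu B positives: 62% at 5% prevalence, 18% to 91% across 30-50% positivity with the same mix, and 44% or 34% at 5% prevalence if 10% or 15% are unreplaced losses.
- Replace the statement that 19 positives give a 10-point margin with expected positives and exact or Wilson 95% limits per pathogen, as in the table above. Say plainly that Flu B is not expected to reach a half-width of 10 points.
- Reconcile the allowance in 14.1 with the total. State that 400 contains about 5% over 380 and that, given the replacement rule in 13.3, this is meant for invalid tests.
- Use Clopper-Pearson or Wilson intervals, not Wald, for the per-pathogen 95% intervals planned in 14.6.

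The cost is protocol wording, with no extra participants; the stated precision for Flu B becomes less favourable. If the sponsor prefers to keep something close to an assurance of 19 Flu B positives, the size at 5% prevalence is 449, 492 or 530 evaluable participants for 80%, 90% or 95% probability. Even then 19 positives would not give the 10-point half-width.
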